11.7 Safety evaluation

The assessment of safety will be based mainly on the frequency of AEs and on the number of laboratory values that fall outside of pre-determined ranges. Other safety data (e.g. ECG, vital signs, and special tests) will be considered as appropriate.

AEs will be summarized by presenting, for each treatment, the number and percentage of patients having any AE and having an AE in each body system. Any other information collected (e.g. severity or relatedness to study medication) will be listed as appropriate.

Laboratory data will be summarized by presenting shift tables using extended normal ranges (baseline to most extreme post-baseline value), by presenting summary statistics of raw data and change from baseline values (means, medians, standard deviations, ranges) and by the flagging of notable values in data listings.

Data from other tests (e.g. ECG or vital signs) will be listed, notable values will be flagged, and any other information collected will be listed as appropriate. If suitable summary statistics will be presented. Any statistical tests performed to explore the data will be used only to highlight any interesting comparisons that may warrant further consideration. Further details will be specified in the analysis plan provided prior to data base lock.

A summary of clinically relevant toxic events, i.e., adverse events that are serious, adverse events or laboratory tests that lead to change of dose of study medication or discontinuation from study medication will be provided.

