6.3 Dose Adjustments

Dose adjustments for both DFP and DFX will be allowed for efficacy reasons (scaling up) or for safety reasons including the presence of markers indicative of over-chelation (scaling down).

DFP can be scaled up in steps of 12.5 mg/kg/day (to a maximum daily dose of 100 mg/kg) according to the individual patient's response defined as an increase of serum ferritin levels > 20% compared to the previous determination.

DFX will be scaled up in steps of 5 to 10 mg/kg (to a maximum daily dose of 40 mg/kg) according to the individual patient's response defined as an increase of ferritin levels > 20% compared to the previous determination.

For patients with a stable serum ferritin value >1500 (no increase or any increase <20%) and not showing a downtrend over a 3-month-period , DFP or DFX can be also increased.

DFP and DFX must be scaled down for the safety reasons detailed in **Table 4**.

Table 4. Scale down adjustment for DFP and DFX (safety reasons)

Serum creatinine increased by >33% from baseline OR Reduction in creatinine clearance (estimated with the Schwartz formula) ≤ 90ml/min and >60 ml/min in two consecutive measurements	No dose adjustment.	Reduce DFX in steps of 10 mg/kg/day until value returns to baseline value and continue DFX with the adjusted dose for 1 month. If the increase persists interrupt DFX. If after DFX interruption value returns to baseline value or > 90 ml/min for creatinine clearance restart DFX at 50% of the last dose and then escalate by 10 mg/kg/day at 1 month intervals provided that value increase does not recur. Monitor serum creatinine, creatinine clearance and urine protein/creatinine ratio weekly (+/- 7 days) during the period of abnormal value and during the first month after dose modification, then monthly.
Urine protein/creatinine ratio ≥ 0.5 in two consecutive measurements	No dose adjustment.	Reduce DFX in steps of 10 mg/kg/day until value returns to < 0.5. If the increase persists interrupt DFX. After the ratio improves, restart DFX at 50% of the last dose and then escalate by 10 mg/kg/day at 1 month intervals provided that value increase does not recur. Monitor serum creatinine, creatinine clearance and urine protein/creatinine ratio weekly (+/- 7 days) during the period of abnormal value and during the first month after dose modification, then monthly.

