7.3.16 Renal function

Renal function will be assessed as serum creatinine and creatinine clearance calculated according to Schwartz formula. Both parameters will be determined at each scheduled study visit (V1 to V15) and weekly (\pm 7 days) during the first month after initiation or modification of therapy.

Serum creatinine for checking exclusion criteria must be assessed in duplicate between day -9 and day -7 of the screening period.

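### The count of out-of-range laboratory values is a main safety measure, but for renal and urine-protein tests it partly reflects retesting ordered for deferasirox only

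*Combined protocol and SAP*

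**What the plan says.** Section 11.7 opens: "The assessment of safety will be based mainly on the frequency of AEs". The second main measure, named in the same sentence, is "the number of laboratory values that fall outside of pre-determined ranges". For adverse events it names the unit, "the number and percentage of patients having any AE and having an AE in each body system". For the laboratory count it names no per-patient unit, no denominator, no restriction to scheduled visits and no rule for repeat tests. A separate summary uses "shift tables using extended normal ranges (baseline to most extreme post-baseline value"). Tests of significance are exploratory: "Any statistical tests performed to explore the data will be used only to highlight any interesting comparisons". Further detail is left to an analysis plan due before database lock.

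The testing rules are elsewhere:

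- **Schedule, both arms.** Table 5 (footnote 5) sets renal tests weekly in the first month and monthly after that. Section 7.3.15 gives urine tests the same pattern.
- **After a dose change, both arms.** Sections 7.3.15 and 7.3.16 add weekly urine and renal tests "during the first month after initiation or modification of therapy".
- **During a renal abnormality, DFX only.** In both renal rows of Table 4 (creatinine or clearance, and urine protein/creatinine ratio) the DFX entry reads "Monitor serum creatinine, creatinine clearance and urine protein/creatinine ratio weekly (+/- 7 days) during the period of abnormal value". It continues this for the first month after a dose modification. The DFP entry in both rows says only that the dose is not adjusted.
- **Neutrophils and liver.** Scheduled neutrophil counts are weekly in both arms, and the neutropenia rows of Table 4 set the same recount interval, every 1-3 days, for both drugs. Transaminases follow one schedule for both (Section 7.3.20).

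**The concern.** A count of abnormal values rises with the number of tests, and rises fastest when the extra tests fall while the result is already abnormal. For creatinine, clearance and urine protein/creatinine ratio, the protocol adds such tests by rule in one arm. Two children with the same renal course would add different numbers to the safety table because of the drug they were assigned.

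The background (Section 3.1) names renal impairment as a known risk of DFX, so renal safety is a comparison that readers will look for. The distortion runs against the comparator and towards the experimental drug.

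**Working it through.** The plan states no figure for laboratory safety, so there is none to reproduce.

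**1. Scheduled renal tests after baseline, each arm.** Weeks 1, 2 and 3, plus the twelve monthly visits V4 to V15: 3 + 12 = 15.

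**2. Values from one renal episode.** For an episode of D weeks, the DFX rule gives about D values and the monthly schedule about D/4.345 (4.345 weeks per month). The ratio is 4.3 at any duration.

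| Episode | DFX, weekly | DFP, monthly | DFX, plus month after one dose change | DFP, same period |
|---|---|---|---|---|
| 4 weeks | 4 | 0.9 | 8 | 1.8 |
| 8 weeks | 8 | 1.8 | 12 | 2.8 |
| 12 weeks | 12 | 2.8 | 16 | 3.7 |

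**3. Effect on the whole arm when the drugs do not differ.** Two arms of 20,000 simulated patients had identical creatinine behaviour. One had the 15 scheduled tests only. The other also had weekly retests after a rise of more than 33% from baseline, continuing for about a month after the last such value. Assumed inputs, none given in the documents: baseline about 0.65 x ULN; 10% or 30% of patients with one episode; duration 4, 8 or 12 weeks; within-patient CV 10% or 15%. Out of range means above ULN. The effect of DFX dose reduction on creatinine was not modelled.

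| Episodes, duration, CV | Tests per patient (scheduled / retested) | Out-of-range values per patient | Ratio |
|---|---|---|---|
| 10%, 8 wk, 10% | 15.00 / 15.63 | 0.412 / 0.588 | 1.43 |
| 10%, 8 wk, 15% | 15.00 / 17.09 | 0.686 / 0.901 | 1.31 |
| 30%, 4 wk, 10% | 15.00 / 15.98 | 0.468 / 0.633 | 1.35 |
| 30%, 4 wk, 15% | 15.00 / 17.40 | 0.735 / 0.957 | 1.30 |
| 30%, 8 wk, 10% | 15.00 / 16.67 | 0.583 / 1.067 | 1.83 |
| 30%, 8 wk, 15% | 15.00 / 18.16 | 0.827 / 1.413 | 1.71 |
| 30%, 12 wk, 10% | 15.00 / 17.31 | 0.685 / 1.474 | 2.15 |
| 30%, 12 wk, 15% | 15.00 / 18.83 | 0.940 / 1.845 | 1.96 |

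**4. Per-patient worst value, same simulation.** The share of patients ever above ULN differs by a ratio of only 1.02 to 1.09 (22.1% against 23.3% with 30% episodes, 8 weeks, CV 10%). The share ever above 1.3 x ULN differs by 1.22 to 1.31 (5.6% against 7.3% in the same case).

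**5. Dividing by the number of tests is not enough.** In that case the rates per test are 0.583/15.00 = 0.0389 and 1.067/16.67 = 0.0640, a ratio of 1.65. The extra tests are concentrated in abnormal periods, so the unit has to be the patient on a common schedule.

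**The case against.** **The laboratory count is one of two main measures, tests are exploratory, and detail is deferred.** All true, so a reader who infers that the safety comparison as a whole reflects testing frequency goes too far: adverse events are summarised by patient. But exploratory status does not remove bias from a descriptive table, and Section 11.7 already states the measure. Its summary of laboratory tests that lead to a dose change is no substitute, because Table 4 prescribes dose changes for these renal findings on DFX only.

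**Neutrophils.** A reader might infer that neutrophil counts are biased as well. The recount rule is the same for both drugs, so counts diverge by arm only if neutropenia itself does. Confirmed neutropenia also follows the SAE notification route (Section 16.6). What remains is a matter of unit: a 14-day episode recounted every 1-3 days gives 5 to 14 values from one child.

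**Dose steps.** A reader might infer that DFX patients collect more tests because their dose range has more steps. The documents do not show this. DFP from 75 to 100 mg/kg/day by 12.5 is two steps, and DFX from 20 to 40 by 10 is also two; four steps arise only at 5 mg/kg each from the lowest start. The weekly tests after a change apply to either drug. Suppose each test had an independent 2.5% chance of a false flag (a rate not in the documents) and each step added three tests. The chance of any flag is 1 - 0.975^k: 31.6% at k = 15, 41.2% at 21 and 49.5% at 27. Two steps on each drug give 41.2% in both arms.

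**Worst-value tables using all data are a legitimate safety choice.** This stands. Such a table takes one value per patient and usually has a triggering value already. Scheduled-only tables have a weakness of their own, since later DFX values may follow a dose reduction.

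**Conclusion.** The point holds for creatinine, creatinine clearance and urine protein/creatinine ratio, and only for those. The retesting rule differs by arm, the stated measure counts values with no patient unit, and the result is tilted against DFX. The per-episode ratio of about 4 follows from the testing rules, if DFP patients stay on the monthly schedule and investigators add no tests. The whole-arm ratio of 1.3 to 2.15 rests on the assumed episode rates, durations and variability, and on a simulation of creatinine alone. The shift table is affected modestly: little at the first threshold, and more at higher grades. Scheduled testing and the neutrophil and liver rules do not differ by arm.

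**What to change.** Change the analysis wording only; testing and treatment rules stay as they are. In Section 11.7 or the later analysis plan:

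1. Make the main laboratory summary the number and percentage of patients with at least one, and with a confirmed, out-of-range value at tests scheduled for both arms. Include the weekly renal and urine tests of month 1 and the weekly neutrophil counts. Define confirmation on scheduled tests, since confirmation by a triggered retest would bring the arm difference back.
2. Show a shift table from scheduled tests beside the planned all-values, most-extreme version.
3. Report the number of tests per patient by arm for each laboratory parameter.

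The cost is one extra set of tables. The scheduled-only version may miss extremes seen only at triggered retests, or may reflect values after DFX was reduced, which is why the all-values version stays.

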9. INTERRUPTION OF TREATMENT

This section deals with a patient's premature withdrawal from the study before completing all scheduled visits. An individual subject may be withdrawn at the discretion of the responsible investigator and the study team for the reasons listed hereby. In the event one or more subjects are withdrawn, additional subjects may be enrolled to ensure an adequate number of subjects complete the cohort.

Reasons that a patient must discontinue participation in a clinical study are considered to constitute one of the following:

1. unsatisfactory therapeutic effect (quarterly increase in ferritin levels of at least 1500 ng/ml as detected by two determinations performed at no more than two weeks interval, or if cardiac MRI T2* decreases under 10ms)
2. subject's condition no longer requires study treatment
3. DFX treatment at 10 mg/kg/day (for safety reasons) for more than 4 weeks
4. DFP or DFX administration suspended (for safety reasons) for more than 4 weeks
5. adverse event(s) requiring change of chelation therapy, including moderate or severe Neutropenia
6. significant protocol violation
7. subject/legal guardian withdrew consent/assent
8. lost to follow-up
9. administrative problems
10. death

In the absence of a medical contraindication or significant protocol violation, the investigator may make an effort to keep the subject in the study. Should a subject withdraw or be withdrawn by the legal guardian, he/she has to complete a full set of the 'end-of-study phase assessments', i.e. a full V16 evaluation. Relevant records will have to be done on the corresponding CRF pages.

This requirement does not refer to patients who passed the screening and washout period and were found not to be eligible for treatment.

Patients prematurely withdrawn from the treatment will be considered treatment failures.

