11.2 Study population

Intent to treat population

For the intent to treat (ITT) analysis all patients that have been randomized and start therapy will be included.

Per protocol population

Patients in the per protocol (PP) population for the primary efficacy analysis (PP1) are those that have received the study drugs and for whom the composite endpoint is available at baseline and after 1 year treatment, without major protocol violations.

For the secondary efficacy evaluation assessed as non-inferiority of DFP to DFX in terms of serum ferritin levels the PP population (PP2) includes only patients for whom the measure of serum ferritin is available at baseline and after 1 year treatment.

For the secondary efficacy evaluation assessed as non-inferiority of DPF to DFX in terms of successfully chelated patients according to cardiac MRI T2* the PP population (PP3) includes only patients for whom the measure cardiac MRI T2* is available at baseline and after 1 year treatment.

Safety population

The population for the safety and tolerability analysis will include all patients having received at least one dose of study medication.

PK and PKPD population

The population for the pharmacokinetic and subsequent exploratory analyses (e.g. correlation between systemic exposure and ferritin levels) will include patients who have received the investigational drugs throughout the duration of the study (i.e., 1 year) and have had a blood sample collected for the assessment of drug concentrations in plasma.

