11.12 Sample Size and power considerations

Primary efficacy objective

Assuming type I and type II errors of 0.025 and 0.20, respectively, and a one-sided test, and under the assumptions that the expected proportion of subjects declared treatment successes in the DFX arm is 65%, and the expected proportion of subjects declared treatment successes in the DFP arm is 67.5% a sample size of 310 subjects, randomized in a 1:1 ratio to DFP or DPX will yield 80% power to demonstrate non-inferiority of DFP versus DFX. Taking into account a possible dropout rate of about 20% a total enrolment of 388 patients aged from 1 month to less than 18 years are expected to be included in the trial.

Secondary efficacy objective

Sample size requirements for the secondary efficacy objectives (non-inferiority in terms of ferritin levels and cardiac MRI T2*) are provided in the following.

Based on published literature, testing for non-inferiority is appropriate also when comparing DFP to DFX efficacy in terms of serum ferritin levels. In this case, considering a hypothesis testing on the continuous measure, a non inferiority margin of 400 ng/ml is considered a reliable estimate of the true allowed maximum difference between the IMPs in order to assume DFP to be non-inferior to DFX in controlling iron overload in patients affected by hereditary haemoglobinopathies. The standard deviation of the differences is available by pooling findings from paediatric studies conducted in Europe and outside (El Alfay M et al., 2010), and a reliable and conservative estimate can be 1000 ng/mL.

On these assumptions, 310 evaluable patients are sufficient to provide at least 90% power to demonstrate non inferiority of DFP to DFX, assuming a type I error of 0.025 and a one-sided test.

When considering efficacy in terms of cardiac MRI T2*, less reliable estimates of treatment efficacy are available, especially in the paediatric population. However, there are no reasons for not assuming at least a non inferiority of DFP to DFX, considering also the known beneficial effects of DFP at the cardiac level. Based on the limited published figures of cardiac MRI T2* in the paediatric population and taking into account adult data, some plausible scenarios of sample sizes and related powers are provided in the following **Table 7**, assuming a type I error of 0.025 and a one-sided test. Detailed power curves will be provided in the statistical plan.

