16. ADVERSE EVENTS (AE) AND SERIOUS ADVERSE EVENTS (SAE) REPORTING

According to ICH E6 Guideline (Good Clinical Practice, GCP), both Investigators and Sponsor follow specific procedures when notifying and reporting adverse events/reactions in clinical trials.

The Principal Investigator or qualified site staff is responsible for detecting, documenting and reporting events that meet the definition of an AE or SAE.

AEs will be collected from the start of Investigational Product and until the follow-up contact. Medical occurrences that begin prior to the start of investigational product but after obtaining informed consent should be recorded separately from the Medical History/Current Medical Conditions CRF.

SAEs will be collected over the same time period as stated above for AEs. However, any SAEs assessed as related to study participation (e.g. investigational product, protocol-mandated procedures, invasive tests, or change in existing therapy) will be recorded from the time a subject consents to participate in the study up to 30 days from last dose or study related invasive procedure. All SAEs will be recorded and reported to Safety Contact (SC) within 24 hours after the Investigator has become aware of the event, as indicated in Section 16.3.

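### No adverse event measure in Section 11.7 accounts for time at risk, so unequal early exit could distort the comparison between arms in either direction

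*Combined protocol and SAP*

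**What the plan says.** Section 11.7 states that "The assessment of safety will be based mainly on the frequency of AEs" and on laboratory values outside set ranges. AEs are shown by treatment as "the number and percentage of patients having any AE and having an AE in each body system". Serious AEs, and AEs or laboratory results that lead to a dose change or discontinuation, get a separate summary. Statistical tests are exploratory, and further detail is left to an analysis plan due before database lock.

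The safety population in Section 11.2 is "all patients having received at least one dose of study medication". Section 11.5 tabulates drug exposure by arm each quarter but does not link it to AE counts. Neither 11.5 nor 11.7 names a patient-year rate or a time-to-event estimate.

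Section 16 says "AEs will be collected from the start of Investigational Product and until the follow-up contact". Under Sections 7.2.3 and 7.2.5 a patient who withdraws has the V16 assessments at withdrawal, so that contact comes early.

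On exits, Section 11.12 reads "Taking into account a possible dropout rate of about 20% a total enrolment of 388 patients" and gives no split by arm. Of the ten reasons in Section 9, item 3 names DFX alone: "DFX treatment at 10 mg/kg/day (for safety reasons) for more than 4 weeks". The others, including moderate or severe neutropenia, are not specific to one arm. In Table 4 the two renal rows and the severe rash row reduce or interrupt DFX and leave deferiprone (DFP) unchanged.

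**The concern.** A percentage of patients with an event is comparable between arms only if the arms are observed for similar lengths of time. Here a patient who leaves at month 3 counts in the denominator like one followed for the whole year, but has far less time in which an AE can be recorded. The plan expects a material number of exits, and it contains routes by which they could be unequal. Item 3 of Section 9 is DFX only, and the DFX-only rows of Table 4 can lead to exit through item 3 or through the shared rule on suspension for more than four weeks (item 4).

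Safety and tolerability is a secondary objective and will weigh in how a non-inferiority result is read. If only percentages are shown, the reader cannot tell how much of a difference between arms reflects event frequency and how much reflects time under observation.

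**Working it through.** **Step 1: the plan's own figures.** Inputs from Section 11.12: success rates 65% (DFX) and 67.5% (DFP), margin 12.5 points, one-sided alpha 0.025, power 80%.

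n per arm = (1.960 + 0.842)² × (0.65×0.35 + 0.675×0.325) / (0.125 + 0.025)² = 7.849 × 0.4469 / 0.0225 = 155.9, so 156 per arm or 312 in total. The plan states 310; power at 155 per arm is 79.8%. For dropout, 310/(1 − 0.20) = 387.5, rounded up to 388, or 194 per arm. The figures reproduce, and the 20% is the plan's own overall allowance.

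**Step 2: exits unrelated to AEs.** Assumptions, none of them from the documents: 12-month AE risk R = 0.30 in both arms, constant hazard L = −ln(1 − 0.30) = 0.357, and a fraction d leaving evenly over the year.

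Crude percentage = (1 − d)R + d[1 − (1 − e^(−L))/L] = 0.300(1 − d) + 0.159d

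Holding overall exit at 20% and varying the split:

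| Exits by arm | Higher-exit arm | Lower-exit arm | Difference |
|---|---|---|---|
| 20% / 20% | 27.2% | 27.2% | 0 |
| 25% / 15% | 26.5% | 27.9% | −1.4 points |
| 30% / 10% | 25.8% | 28.6% | −2.8 points |
| 40% / 0% | 24.4% | 30.0% | −5.6 points |

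If every exit falls at month 3, the differences are 0, −2.2, −4.3 and −8.6 points. With even exits, the range from equal loss to 40%/0% is 0 to 2.0 points at a 10% risk and 0 to 8.9 points at a 50% risk.

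A rate removes this. At 30%/10%, time at risk to first event is 0.2577/0.357 = 0.722 years per patient in one arm and 0.2859/0.357 = 0.802 in the other. Both give 35.7 first events per 100 patient-years.

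**Step 3: exits caused by the AE.** Keep the 30% background risk and exits of 30% v 10%, but let the excess be AE-caused. Constant hazards: background AE 0.357, other exits −ln(0.9) = 0.105, AE-caused exit 0.357 − 0.105 = 0.251 (higher-exit arm only).

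- Any AE, higher-exit arm: (0.357 + 0.251)/0.713 × (1 − e^(−0.713)) = 43.5%
- Any AE, lower-exit arm: 0.357/0.462 × (1 − e^(−0.462)) = 28.6%
- AEs other than the exit-causing type: 0.357/0.713 × 0.51 = 25.5% v 28.6%

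So the higher-exit arm looks worse on any AE. In this scenario it is worse: with complete follow-up the figures would be 1 − e^(−0.608) = 45.6% v 30%. The other AE types are still understated, by 3.1 points.

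**Step 4: scale.** The 95% half-width for a difference at 30% risk and 194 per arm is 1.96 × √(2×0.3×0.7/194) = 9.1 points. It is 6.0 points at 10% risk and 10.0 at 50%.

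**The case against.** The strongest objection is about direction. A reader might infer that the arm losing more patients will look safer. The documents do not support that as a general statement. The arm-specific exits they describe are safety exits, where the triggering event is normally recorded before the patient leaves. Step 3 shows that such an arm can look worse on any AE. The inference holds only for exits unrelated to AEs and for other AE types that would have occurred later. This part of the objection stands in full.

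The size can also be challenged. The 20% is one overall figure, equal loss gives no bias, and every unequal split above is assumed. Only one of the ten exit reasons is specific to an arm. The Table 4 rows are dose rules that reach exit only indirectly. Section 11.13 expects little missing data. The even-exit differences at 30% risk are all below the 9.1-point half-width. All of this limits the importance of the point.

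Finally, the plan is not blind to exposure. It tabulates exposure by arm, summarises AEs leading to discontinuation, treats safety comparisons as descriptive and leaves detail to a later plan. Under Section 16, related serious events are recorded for up to 30 days after the last dose, and patients with serious events are followed to recovery or stabilisation. Patients with moderate or severe neutropenia are monitored to resolution (Section 7.3.18). These provisions help, but none restores the routine AE observation lost after withdrawal. Separate exposure and AE tables do not give a rate, and the deferral to a later plan does not promise one.

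**Conclusion.** The point holds as a minor, inexpensive improvement. The stated AE measure takes no account of time at risk, although the plan expects about 20% to leave and has exit routes that could differ by arm. Under the Step 2 assumptions the bias runs from 0 points with equal loss to 5.6 points at 40%/0%, with 1.4 and 2.8 points for the intermediate splits. These figures rest on an assumed 30% risk, a constant hazard, exits spread evenly over the year and unrelated to AEs, and assumed arm splits. The documents fix neither the size nor the sign of any difference in exits, so no claim that either drug would be favoured is justified. The bias differs by event type: exit-causing events are largely captured and other events are understated. Percentages alone therefore do not tell the reader which way they mislead. Sample size and the primary analysis are unaffected.

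**What to change.** Keep the percentages and add the following to Section 11.7, or to the analysis plan it refers to, before database lock:

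- AE incidence per 100 patient-years by arm for any AE, serious AEs, neutropenia, renal events and hepatic events. Time at risk runs from first dose to the first such event or the end of AE collection.
- Cumulative incidence by arm of neutropenia and of AE-related discontinuation, with other exits treated as competing events.
- Time on study by arm and by reason for exit.

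The three should be read together. Patient-year rates assume a roughly constant hazard and that patients who leave would have had the same later risk as those who stay. The cumulative incidence curves show timing. Their 12-month value is not itself corrected for unequal exit: if exits are the only incomplete follow-up, it equals the crude percentage. The exit table shows whether unequal loss is present at all.

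The cost is some wording and a few tables, with no new visits and no change to sample size or to any clinical rule. The sponsor should confirm that AE start dates and the date of last AE contact are captured, since Section 11.5 covers only drug exposure and dose changes.
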